3.5.4 Adverse events

AEs will be collected throughout the study, from date of informed consent until 30 days after the last dose of study treatment. Any events in this period that occur after a patient has received further therapy for cancer (following discontinuation of study treatment) will be flagged in the data listings.

Adverse events will be defined as treatment emergent if they onset, or worsen (by investigator report of a change in intensity), during the study treatment period (defined from date of first dose of any study treatment to date of last dose of any study treatment) or safety follow-up period (30 days after last dose of study treatment).

The Medical Dictionary for Regulatory Activities (MedDRA) will be used to code the AEs. AEs will be graded according to the National Cancer Institute Common Terminology Criteria for AEs (CTCAE Version 4.03).

Other significant adverse events

During the evaluation of the AE data, an AstraZeneca medically qualified expert will review the list of AEs that were not reported as serious adverse events (SAEs) and 'Discontinuation of Investigational Product due to Adverse Events' (DAEs). Based on the expert's judgement, significant adverse events of particular clinical importance may, after consultation with the Global Patient Safety Physician, be considered other significant adverse events (OAEs) and reported as such in the CSR. A similar review of laboratory/vital signs/ECG data will be performed for identification of OAEs.

AEs of special interest

The following AEs of special interest (AESIs) have been identified by the patient safety team and included in the study protocol:

AESIs for Olaparib are myelodysplastic syndrome (MDS), acute myeloid leukaemia (AML), new primary malignancy (other than MDS/AML) and pneumonitis.

Other categories may be added as necessary or existing terms may be merged. An AstraZeneca medically qualified expert after consultation with the Global Patient Safety Physician has reviewed the AEs of interest and identified which higher-level terms and which preferred terms contribute to each AESI. Further reviews may take place prior to database lock (DBL) to ensure any further terms not already included are captured within the categories.

There are no AESIs for AZD1775 or AZD6738 which require additional data collection.

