4.3 Follow-up period

Assessments at the end of the treatment period will be conducted 30 days (+7 days) after the last dose of study treatment according to Study Plan (see [Table 4](#) and [Table 5](#)).

Survival follow-up will be conducted approximately every 8 weeks (± 7 days) after the 30-day follow-up visit according to Study Plan (see [Table 4](#) and [Table 5](#)).

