6.3 Recording of AEs

6.3.1 Time period for collection of AEs

Adverse events (including SAEs) will be collected from *time of signature of informed consent* throughout the treatment period and including the follow-up period (ie, through the 30-day follow-up visit). All SAEs related to clinical trial procedures are to be recorded from the signing of Screening Part 1 ICFs and all AEs and SAEs are to be recorded from the signing of Screening Part 2 ICFs.

After any interim analysis, any ongoing AEs/SAEs need to be unlocked and followed for resolution.

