6.3.1.1 Adverse events after the 30-day follow-up period

For Pharmacovigilance purposes and characterisation, any case of MDS/AML or new primary malignancy occurring after the 30-day follow up period should be reported to AstraZeneca Patient Safety whether it is considered a non serious AE (eg non melanoma skin cancer) or SAE, and regardless of Investigator's assessment of causality or knowledge of the treatment arm. Investigators will be asked during the regular follow up for OS if the patient has developed MDS/AML or a new primary malignancy and prompted to report any such cases.

If the investigator becomes aware of a SAE with a suspected causal relationship to the investigational medicinal product that occurs after the end of the clinical study in a participant treated by him or her, the investigator shall, without undue delay, report the serious adverse event to the sponsor.

If patients who are gaining clinical benefit are allowed to continue study treatment post data cut off and/or post study completion then all SAEs must continue to be collected and reported to Patient Safety within the usual timeframe.

Otherwise, after study treatment completion (ie, after any scheduled post treatment follow-up period has ended) there is no obligation to actively report information on new AEs or SAEs occurring in former study patients. This includes new AEs/SAEs in patients still being followed up for survival but who have completed the post treatment follow up period (30 days).

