8.4.2 Secondary outcome measures (Calculation or derivation of safety variables)

Safety and tolerability will be assessed in terms of AEs, deaths, laboratory data, vital signs, ECG data and ECOG PS. These will be collected for all patients.

Adverse events

AEs (both in terms of Medical Dictionary for Regulatory Activities [MedDRA] preferred terms and CTCAE grade) will be listed individually by patient.

Any AE occurring within 28 days of discontinuation of IP will be included in the AE summaries. Any events in this period that occur after a patient has received further therapy for cancer (following discontinuation of IP) will be flagged in the data listings.

Other significant AEs (OAEs)

During the evaluation of the AE data, an AstraZeneca medically qualified expert will review the list of AEs that were not reported as SAEs and AEs leading to discontinuation. Based on the expert's judgement, significant AEs of particular clinical importance may, after consultation with the Global Patient Safety Physician, be considered OAEs and reported as such in the CSR. A similar review of laboratory/vital signs (pulse and BP)/ECG data will be performed for identification of OAEs.

Examples of these could be marked haematological and other laboratory abnormalities, and certain events that lead to intervention (other than those already classified as serious), dose reduction or significant additional treatment.

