4.2.10 Analysis of safety and tolerability data

4.2.10.1 Analysis of adverse events

Summary tables mentioned below will include all treatment emergent AEs (as defined in Section 3.5.4). Any events in this period that occur after a patient has received further therapy for cancer (following discontinuation of study treatment) will be flagged in AE data listings.

Summaries by treatment arm, displaying MedDRA System Organ Class (SOC) and Preferred Term (PT) of treatment emergent AEs will include number (%) of patients who have:

- At least one AE (for All patient population and each of the 3 primary patient populations)
- At least one AE with CTCAE grade ≥ 3 (for All patient population and each of the 3 primary patient populations)
- At least one AE by maximum CTCAE grade
- At least one AE causally related to study medication (separately for investigational product in the combination treatment arms)
- At least one AE with CTCAE grade ≥ 3 causally related to study medication (separately for investigational product in the combination treatment arms)
- At least one AE leading to discontinuation of study treatment (for All patient population and each of the 3 primary patient populations)
- At least one OAE
- At least one SAE (for All patient population and each of the 3 primary patient populations)
- At least one SAE causally related to study medication (separately for investigational product in the combination treatment arms)

An overall summary of the number and percentage of patients in each category bulleted above will be presented, as well as an overall summary of the number of events in each category. In addition, a truncated AE table of most common AEs, showing all PTs that occur in at least 5% of patients overall will be summarised by preferred term, by decreasing frequency. This cut-off may be modified after review of the data.

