4.2.10.2 Analysis of adverse events of special interest

A listing of the MedDRA Preferred Terms used for each AESI category will be provided by AZ and will be attached as an Appendix to the SAP.

Summaries by AESI category will include number (%) of patients who have:

- At least one AESI by maximum CTCAE grade
- At least one AESI leading to discontinuation of study treatment.

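### The SAP's 30-day adverse-event window leaves non-fatal late MDS/AML and new primary malignancies without a place in the AESI summary, and the protocol and SAP state different AE summary windows

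*SAP*

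**What the plan says.** Protocol 6.1.1 names MDS/AML, new primary malignancy and pneumonitis as the olaparib AESIs, and SAP 3.5.4 repeats the list. For the first two, Protocol 6.3.1.1 extends reporting: "any case of MDS/AML or new primary malignancy occurring after the 30-day follow up period should be reported to AstraZeneca Patient Safety". It adds that investigators will be prompted about them during the regular survival follow-up, which Protocol 4.3 schedules about every 8 weeks. Pneumonitis is not part of this late reporting.

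SAP 3.5.4 sets the general window: "AEs will be collected throughout the study, from date of informed consent until 30 days after the last dose of study treatment". It defines an event as treatment-emergent if it starts or worsens during treatment "or safety follow-up period (30 days after last dose of study treatment"). SAP 4.2.10.1 then says: "Summary tables mentioned below will include all treatment emergent AEs (as defined in Section 3.5.4"). SAP 4.2.10.2, which follows, lists patients with "At least one AESI by maximum CTCAE grade" and those whose AESI led to discontinuation. It gives no time window of its own, and neither does the title of T 11.3.2.15.

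On the general AE window, Protocol 8.4.2 says: "Any AE occurring within 28 days of discontinuation of IP will be included in the AE summaries". Protocol 6.3.1 has collection "including the follow-up period (ie, through the 30-day follow-up visit"), and Protocol 4.3 times that visit: "Assessments at the end of the treatment period will be conducted 30 days (+7 days) after the last dose of study treatment". SAP Section 6 marks changes from the protocol as not applicable.

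**The concern.** Two things are at stake.

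First, the protocol goes out of its way to find two named safety outcomes after treatment has ended, yet the analysis plan has no output defined to receive them. A programmer following the SAP would apply the only window it defines. The study report could then show few or no cases of MDS/AML or new primary malignancy by arm while Patient Safety holds reports of them, including for the ceralasertib+olaparib combination.

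Second, the two documents give different end points for the routine AE summaries, and the SAP does not record the difference.

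**Working it through.** There is no stated figure to reproduce. The check compares windows, followed by one illustration.

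**Step 1. Trace a late case.** Take a non-fatal new primary malignancy with onset 100 days after last dose.
- Protocol 6.3.1.1: reportable to Patient Safety and prompted at survival contacts.
- SAP 3.5.4: outside AE collection (100 > 30) and not treatment-emergent.
- SAP 4.2.10.1: outside the summary tables.
- SAP 4.2.10.2 and T 11.3.2.15: no exception brings it back.
- SAP 4.2.10.3: not applicable, because the case is not fatal. A fatal AE at or after 30 days does have a row there.
- Data source: Protocol 6.3.1.1 names Patient Safety and does not mention the eCRF. For patients in survival follow-up after the PFS cut-off, Protocol 9.3 names survival and subsequent cancer therapy as the continuing eCRF items.

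The case therefore has no defined place in the AESI summary.

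**Step 2. Compare the general windows.**

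| Source | End of window |
|---|---|
| Protocol 8.4.2, summaries | day 28 after discontinuation of IP |
| SAP 3.5.4, collection and summaries | day 30 after last dose |
| Protocol 6.3.1 with 4.3, collection | the follow-up visit, days 30 to 37 |

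Onsets on days 29 and 30 are in the SAP's summaries and out of the protocol's. Onsets from day 31 to the visit are collected under the protocol and summarised under neither document.

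**Step 3. How much the visit timing matters.** Inclusion follows the date of onset or worsening. For a visit on day v, the share of post-dose onset days beyond the SAP window is (v − 30)/v. The maximum is 7/37 = 18.9%, at v = 37. The mean over v = 30, …, 37 is (0 + 1/31 + 2/32 + 3/33 + 4/34 + 5/35 + 6/36 + 7/37)/8 = 10.0%. Only an event dated to the visit day itself is usually outside: 7 of the 8 permitted days (87.5%) fall after day 30.

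**Step 4. Illustration of follow-up outside the AESI window.** The documents give no survival assumption, so the following is assumed: exponential times, median OS 12 to 24 months, and treatment ending at progression. Median PFS is taken from the sample-size section: 5 or 6 months on olaparib, and 5 + 4.17 = 9.17 or 6 + 5 = 11 months on the combination. Follow-up T runs from 42 − 15 = 27 months to 42 months (OS analysis at about 42 months, 15 months' recruitment).

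Mean time up to T with median m: R(m, T) = (1 − exp(−λT))/λ, where λ = ln 2/m.
Share of patient-time alive after the window: 1 − (R(PFS, T) + 30/30.4)/R(OS, T).

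Example with T = 42, PFS 6, OS 18: R(6, 42) = 8.59, R(18, 42) = 20.8, share = 1 − (8.59 + 0.99)/20.8 = 0.54. With PFS 11 and the same OS, the share is 0.24.

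Over the whole grid the share is 32% to 66% at median PFS 5 to 6 months, and about 0% to 44% at 9.17 to 11 months.

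**The case against.** The strongest reply is that the exclusion is not written anywhere. The treatment-emergent restriction sits in SAP 4.2.10.1, while 4.2.10.2 and the title of T 11.3.2.15 are silent. That is correct, and the point is put as an inference. But 30 days is the only AE window the SAP defines, and SAP 3.5.4 says collection itself stops there. At best the AESI window is unspecified.

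A second reply is that late cases are reported for pharmacovigilance and were never meant for the AE tables; Protocol 8.4.2 is narrower still and has no AESI exception. This also stands in part: Protocol 6.3.1.1 does not route the cases to the clinical database. It is why the fix must name a data source. It does not explain why a study report should omit known cases of a named AESI. The SAP already reports beyond 30 days for fatal AEs.

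A third reply concerns timing. SAP 2.0 (14 June 2019) was aligned to Protocol 6.0, whereas the protocol reviewed is 7.0 (6 May 2020), and its version history lists updated wording for 6.3.1.1. A reader might infer that SAP Section 6 was wrong to declare no change on late AESIs. The documents do not support that, because the 6.0 wording is not available. The 28- versus 30-day difference is another matter: the version history lists no later change to 8.4.2.

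**Conclusion.** The point holds on two counts. Non-fatal MDS/AML and new primary malignancies arising more than 30 days after last dose have no defined place in the planned AESI summary, which could understate them. And the AE summary window is 28 days in the protocol and 30 in the SAP, without acknowledgement. The first count rests on reading SAP 3.5.4, 4.2.10.1 and 4.2.10.2 together; the second needs no assumption. Both affect safety reporting, not the primary endpoint.

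The size of the first count cannot be fixed from the documents. The 32% to 66% figure is patient-time under assumed survival and not a share of missed cases. It also ends treatment at progression, although Protocol 3.8 allows continuation beyond it. It shows only that the follow-up outside the window may be large, and may differ between arms if one stays on treatment longer.

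Three stronger readings are tempting but unsupported:
- **That most findings at the 30-day visit are lost.** Inclusion depends on onset or worsening, so only onsets on days 31 to 37 fall outside the SAP window. Laboratory, vital-sign and ECG results also have their own outputs in SAP 4.2.10.4 to 4.2.10.6, which state no 30-day limit.
- **That T 11.3.2.16 loses cases too.** It covers AESIs leading to discontinuation of olaparib, and an event arising more than 30 days after the last dose cannot do that.
- **That the protocol follows these events because they arise late by nature.** Protocol 6.3.1.1 gives pharmacovigilance and characterisation as its purpose.

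**What to change.** 1. In SAP 3.5.4 and 4.2.10.2, add a by-arm summary of all MDS/AML and new primary malignancy cases from first dose to data cut-off, whatever the time since last dose, split into onset within and after 30 days. Name the source as Patient Safety cases reconciled to the clinical database.
2. Use one AE summary window in both documents: either change 28 days in Protocol 8.4.2 to the SAP's 30, or list the difference in SAP Section 6.
3. State how an AE with onset between day 30 and the actual follow-up visit is handled. Extending the treatment-emergent window to the visit is one option, but that is a preference and not required.

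The cost is SAP wording, one extra table or column and a one-line protocol correction, with no new visits or assessments. Reconciliation is a small added step: Protocol 9.4 already reconciles SAEs with the Patient Safety database, but late non-serious cases, such as some skin cancers, would need to be added. The AESI counts may look less favourable.

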3.5.5 Safety laboratory test results

Continuous local safety laboratory test results (see study protocol Table 5) will be converted to values in International System of Units (Système international d'unités, SI) units in the clinical database. The test results in SI units will be exported from the clinical database, together with the original test results/units reported by the sites. The specific choice of the SI unit for the safety laboratory test results (as well as the respective conversion factors) will follow the most recent AZ Labcodes_plus_CDISC file. Exceptions are liver function tests alanine aminotransferase [ALT], aspartate aminotransferase [AST], gamma-glutamyl transpeptidase [GGT]) for which IU/L will be used rather than the SI unit ukat/L.

3.6 Secondary outcome measures (derivation of PK variables)

The minimum concentrations at steady state ($C_{\min ss}$) will be derived from the drug concentration data for Olaparib, AZD6738 and AZD1775, and provided to PAREXEL Biostatistics.

Given the sparse PK schedule, other PK parameters will be derived using population PK modelling described in a separate analysis plan. The results of any such analyses will be reported separately from the CSR.

3.7 Exploratory outcome measures (CCI [REDACTED])

Not applicable as CCI [REDACTED] will not be analysed by PAREXEL.

4. ANALYSIS METHODS

4.1 General principles

4.1.1 Use of analysis sets

Study population, demography, efficacy and CCI [REDACTED] data will be summarised based upon the FAS.

Safety and study treatment exposure data will be summarised based upon the SAF.

Study drug concentration and PK data will be summarised based upon the PK analysis set.

4.1.2 Handling of 3 treatment arms in the outputs

All outputs (tables, figures, listings) will display all 3 treatment arms. Only tables for study population, disposition and demographics will include an overall column displaying pooled results.

In the outputs, the three treatment arms will be labelled as:

- “Olaparib” for treatment arm Olaparib monotherapy
- “AZD6738+Olaparib” for treatment arm AZD6738 + Olaparib
- “AZD1775+Olaparib” for treatment arm AZD1775 + Olaparib

4.1.3 Definition of baseline and change from baseline

The baseline value will be defined differently for efficacy and safety analyses:

- For efficacy (including CCI), baseline value will be the last value obtained prior to randomisation. Note the following instructions:
 - If there are two assessments on the same last day prior to the randomisation, one with time recorded and the other without time recorded, the one with time recorded would be selected as baseline value.
 - Assessments on the day of randomization where no time is captured will be considered prior to randomization if such procedures are required by the protocol to be conducted before randomization.
 - If an evaluable assessment is only available after randomization but before the first dose of study treatment then this assessment will be used as baseline value.
 - In listings or figures displaying individual efficacy data over time, study day will be calculated in relation to date of randomization (= Study Day 1).
- For safety, baseline value will be the last value obtained prior to the first dose of study treatment. Note the following instructions:
 - If there are two assessments on the same last day prior to the first dose of study treatment, one with time recorded and the other without time recorded, the one with time recorded would be selected as baseline value.
 - Assessments on the day of the first dose of study treatment where no time is captured will be considered prior to the first dose of study treatment if such procedures are required by the protocol to be conducted before the first dose of study treatment.
 - In listings or figures displaying individual safety data over time, study day will be calculated in relation to date of first treatment (= Dose Day 1).

Absolute change from baseline will be calculated as post-treatment value minus baseline value. Percentage change from baseline will be calculated as (post-baseline value minus baseline value) divided by baseline value multiplied by 100. Percentage change from baseline will not be used for variables for which the baseline value can be equal to 0.

4.1.4 Time windows for summaries by visit

Visit windows will be used for any presentations that summarise values by visit. The following conventions will be applied:

- The window for visit D1 (at the day of first intake of study medication but assessments to be done prior to that first intake) is limited to Dose Day 1.
- The windows for post-baseline visits are constructed in such a way that the upper limit of the interval falls half way between the two visits. If an odd number of days exists between two consecutive visits then the upper limit is taken as the midpoint value minus 1 day.
- Visit windows are exhaustive so that all unscheduled visit data have the potential to be included in the visit windows.
- Inclusion of data within a visit window is based on actual assessment/visit date and not intended assessment/visit date.

Table 4 VIOLETTE visit windows using a calendar days / weeks metric

(SP = Screening Period D = Day W = Week CCI)

Treatment arms Olaparib and AZD6738+Olaparib with cycle length 28 days		Treatment arm AZD1775+Olaparib with cycle length 21 days	
Visit window label	Visit window	Visit window label	Visit window
SP1	> 28 days prior to Dose Day 1	SP1	>28 days prior to Dose Day 1
SP2	[28 days prior to Dose Day 1; 1 day prior to Dose Day 1]	SP2	[28 days prior to Dose Day 1; 1 day prior to Dose Day 1]
D1	Dose Day 1 (exact)	D1	Dose Day 1 (exact)
D7	[1 day after Dose Day 1; 9 days after Dose Day 1]	–	–
–	–	D10	[1 day after Dose Day 1; 11 days after Dose Day 1]
D15	[10 days after Dose Day 1; 20 days after Dose Day 1]	D15	[12 days after Dose Day 1; 16 days after Dose Day 1]
–	–	W3 / D22	[17 days after Dose Day 1; 31 days after Dose Day 1]
W4 / D29	[21 days after Dose Day 1; 41 days after Dose Day 1]	–	–
–	–	W6 / D43	[32 days after Dose Day 1; 52 days after Dose Day 1]
W8 / D57 (except scan, CCI)	[42 days after Dose Day 1; 69 days after Dose Day 1]	–	–
W8 / D57 (only scan, CCI)	[1 day after Dose Day 1; 83 days after Dose Day 1]	W8 / D57 (only scan, CCI)	[1 day after Dose Day 1; 83 days after Dose Day 1]
–	–	W9 (D64)	[53 days after Dose Day 1; 73 days after Dose Day 1]
W12 / D85	[70 days after Dose Day 1; 97 days after Dose Day 1]	W12 / D85	[74 days after Dose Day 1; 94 days after Dose Day 1]

Treatment arms Olaparib and AZD6738+Olaparib with cycle length 28 days		Treatment arm AZD1775+Olaparib with cycle length 21 days	
Visit window label	Visit window	Visit window label	Visit window
–	–	W15 / D106	[95 days after Dose Day 1; 115 days after Dose Day 1]
W16 / D113 (except scan, CCI)	[98 days after Dose Day 1; 125 days after Dose Day 1]	–	–
W16 / D113 (only scan, CCI)	[84 days after Dose Day 1; 139 days after Dose Day 1]	W16 / D113 (only scan, CCI)	[84 days after Dose Day 1; 139 days after Dose Day 1]
–	–	W18 / D127	[116 days after Dose Day 1; 136 days after Dose Day 1]
W20 / D141	[126 days after Dose Day 1; 153 days after Dose Day 1]	–	–
–	–	W21 / D148	[137 days after Dose Day 1; 157 days after Dose Day 1]
W24 / D169 (except scan, CCI)	[154 days after Dose Day 1; 181 days after Dose Day 1]	W24 / D169 (except scan, CCI)	[158 days after Dose Day 1; 178 days after Dose Day 1]
W24 / D169 (only scan, CCI)	[140 days after Dose Day 1; 195 days after Dose Day 1]	W24 / D169 (only scan, CCI)	[140 days after Dose Day 1; 195 days after Dose Day 1]
and so on			

Table 5 VIOLETTE visit windows using a cycle metric

(SP = Screening Period C = Cycle D = Day)

Treatment arms Olaparib and AZD6738+Olaparib with cycle length 28 days		Treatment arm AZD1775+Olaparib with cycle length 21 days	
Visit window label	Visit window	Visit window label	Visit window
SP1	> 28 days prior to Dose Day 1	SP1	>28 days prior to Dose Day 1
SP2	[28 days prior to Dose Day 1; 1 day prior to Dose Day 1]	SP2	[28 days prior to Dose Day 1; 1 day prior to Dose Day 1]
C1 D1	Dose Day 1 (exact)	C1 D1	Dose Day 1 (exact)
C1 D7	[1 day after Dose Day 1; 9 days after Dose Day 1]	–	–
–	–	C1 D10	[1 day after Dose Day 1; 11 days after Dose Day 1]
C1 D15	[10 days after Dose Day 1; day before first dosing in Cycle 2]	C1 D15	[12 days after Dose Day 1; day before first dosing in Cycle 2]
C2	[day of first dosing in Cycle 2; day before first dosing in Cycle 3]	C2	[day of first dosing in Cycle 2; day before first dosing in Cycle 3]
C3	[day of first dosing in Cycle 3; day before first dosing in Cycle 4]	C3	[day of first dosing in Cycle 3; day before first dosing in Cycle 4]

Treatment arms Olaparib and AZD6738+Olaparib with cycle length 28 days		Treatment arm AZD1775+Olaparib with cycle length 21 days	
Visit window label	Visit window	Visit window label	Visit window
and so on			

The timing of scan visits (including **CCI** is not cycle-based; hence they are not included in the Table 5.

For visit based summaries, the following convention will be applied:

- If there is more than one value per patient within a time window then the closest value to the scheduled visit date is summarised, or the earlier, in the event the values are equidistant from the nominal visit date. The listings highlight the value for the patient that contributed to the summary table, wherever feasible.

